10.5.2 Safety objectives

10.5.2.1 Analysis set and grouping for the analyses

For all safety analyses, the safety set will be used. All listings and tables will be presented by treatment group and tumor types.

The overall observation period will be divided into three mutually exclusive segments:

1. Pre-treatment period: from day of patient's informed consent to the day before first dose of study treatment
2. On-treatment period: from day of first dose of study medication to 30 days after last dose of study treatment
3. Post-treatment period: starting at day 31 after last dose of study treatment.

Safety summaries will primarily be based on all data from the on-treatment period. Following last administration of study treatment, adverse events (including serious adverse events), and new antineoplastic therapies are collected for a period of 150 days. Following start of new antineoplastic therapy only treatment related adverse events will be collected. Select summaries of related adverse events will be produced for the combined on-treatment and post-treatment periods (see [Section 10.5.2.2](#)).

10.5.2.2 Adverse events (AEs)

Summary tables for adverse events (AEs) will include only AEs that started or worsened during the on-treatment period, the **treatment-emergent** AEs. Additional select summaries will be produced using all related AEs that started or worsened during the combined on-treatment and post-treatment periods.

The incidence of treatment-emergent adverse events (new or worsening from baseline) will be summarized by system organ class and or preferred term, severity (based on CTCAE grades), type of adverse event, relation to study treatment by tumor type and treatment group.

Serious adverse events, non-serious adverse events and adverse events of special interest (AESI) during the on-treatment period will be tabulated.

All deaths (on-treatment and post-treatment) will be summarized.

All AEs, deaths and serious adverse events (including those from the pre and post-treatment periods) will be listed and those collected during the pre-treatment and post-treatment period will be flagged.

All safety data from the patients from Japanese safety run-in part will be summarized separately. More details will be provided in the SAP.

10.5.2.3 Laboratory abnormalities

Grading of laboratory values will be assigned programmatically as per CTCAE version 4.03. The calculation of CTCAE grades will be based on the observed laboratory values only, clinical assessments will not be taken into account.

CTCAE Grade 0 will be assigned for all non-missing values not graded as 1 or higher. Grade 5 will not be used.

For laboratory tests where grades are not defined by CTCAE 4.03, results will be categorized as low/normal/high) based on laboratory normal ranges.

The following summaries will be generated separately for hematology, and biochemistry tests:

- Listing of all laboratory data with values flagged to show the corresponding CTCAE 4.03 grades if applicable and the classifications relative to the laboratory normal ranges

For laboratory tests where grades are defined by CTCAE 4.03:

- Worst post-baseline CTCAE grade (regardless of the baseline status). Each patient will be counted only once for the worst grade observed post-baseline.
- Shift tables using CTCAE 4.03 grades to compare baseline to the worst on-treatment value

For laboratory tests where grades are not defined by CTCAE 4.03:

- Shift tables using the low/normal/high/ (low and high)
- Classification to compare baseline to the worst on-treatment value.

10.5.2.4 Other safety data

ECG

- Shift table baseline to worst on-treatment result for overall assessments
- Listing of ECG evaluations for all patients with at least one abnormality

Vital signs

Definitions of notably abnormal results will be specified in the SAP.

- Shift table baseline to worst on-treatment result

10.5.2.5 Supportive analyses for secondary objectives

Any supportive analyses that are considered appropriate for secondary variables will be described in the SAP prior to database lock (DBL).

10.5.2.6 Tolerability

Tolerability of study drug treatment will be assessed by summarizing the number of treatment dose interruptions and dose reductions. Reasons for dose interruption and dose reductions will be listed by patient and summarized.

10.5.3.1 Outline of the data analysis

As a project standard, the data collected from tumor samples in the clinical database will be analyzed by a Novartis designated laboratory and Novartis Oncology study team.

If the number of samples is inadequate to perform a rigorous data analysis, then only the available data will be listed. Additional analyses that may be performed after the completion of the end-of-study clinical study report will be documented in separate reports. Any additional data analysis will be described in an addendum of the RAP or in a stand-alone analysis plan document, as appropriate.

10.5.3.2 Data handling principles

All measurements below their respective Lower Limit of Quantification (LLOQ) or missing data will be labeled as such in the concentration data listings. Measurements below the LLOQ will be treated as zero in summary statistics. Change from baseline analyses will only be performed on patients with measurable samples and pre- and post-treatment time points.

10.5.3.3 Data analysis principles

10.5.3.3.1 Analysis sets

Patients with measureable tumor samples will be identified in the summaries and relevant proportion will be calculated against this number of patients.

[REDACTED]

10.5.3.3.3 Advanced analysis methods

Any methods that may be used will be described in the SAP.

10.5.4 Pharmacokinetics

All patients who have evaluable PK data will be included in the PK data analysis. PK parameters will be determined using non-compartmental method(s) for NIR178 and its metabolite and PDR001. PK parameters such as those listed in [Table 10-2](#) will be estimated and reported, when applicable. [REDACTED]

[REDACTED]

Table 10-2 Noncompartmental pharmacokinetic parameters

AUClast	The AUC from time zero to the last measurable concentration sampling time (tlast) (mass x time x volume-1)
AUCinf	The AUC from time zero to infinity (mass x time x volume-1)
AUCtau	The AUC calculated to the end of a dosing interval (tau) at steady-state (amount x time x volume-1)
Cmax	The maximum (peak) observed plasma, blood, serum, or other body fluid drug concentration after single dose administration (mass x volume-1)
Tmax	The time to reach maximum (peak) plasma, blood, serum, or other body fluid drug concentration after single dose administration (time)
T1/2	The elimination half-life associated with the terminal slope (λ_z) of a semi logarithmic concentration-time curve (time). Use qualifier for other half-lives
CL/F	The total body clearance of drug from the plasma (volume x time-1)
Vz/F	The apparent volume of distribution during terminal phase (associated with λ_z) (volume)

10.5.4.1 Data handling principles

Only PK blood samples with the date and time and for which the last prior dose dates and times are adequately recorded will be included in the PK analyses. Missing concentration values will be reported as is in data listings. Concentration values below Lower limit of quantitation (LLOQ) will be handled as zero in summary statistics, and reported as is in data listings. Any missing pharmacokinetic parameter data will not be imputed.

10.5.4.1.1 Basic tables, figures and listings

Descriptive statistics (mean, standard deviation, CV% or median (range)) will be presented for all parameters by analyte, tumor types and treatment groups and study cycle/day. When a geometric mean is presented, it will be stated as such. Zero concentrations will not be included in the geometric mean calculation. Since Tmax is generally evaluated by a nonparametric method, median values and ranges will be presented for this parameter. For NJI765, CL/F, Vz/F and elimination half-life will not be reported.

PK data for Japanese safety run-in part will be reported separately.

[REDACTED]

[REDACTED]

10.5.5 Resource utilization

Not applicable.

[REDACTED]

10.5.6 Patient-reported outcomes

Not applicable.

10.7 Interim analysis

Part 1:

Patients will be continuously accrued and the data will be analyzed using a Bayesian hierarchical model mentioned in [Section 10.4.2](#). Interim analysis for a tumor type will be performed when at least 10 patients which have been enrolled for that tumor type at the same dose level have at least one post-baseline disease assessment, except for MSS-CRC RAS wildtype, MSS-CRC RAS mutant and RCC IO naive at 240 mg patients, in which no interim analysis will be done. The futility analysis will not be binding. At each of these analyses, the current (posterior) probability that the response rate for each of the tumor types is greater than “clinically meaningful threshold (column for C2 in [Table 10-1](#))” will be determined.

These probabilities will be used to adapt the design. All available data for evaluable patients (defined in [Section 10.4.3](#)) will be used for analysis at each interim analysis. However, a decision will be made for all tumor types with minimum of 10 patients (who have at least one post-baseline assessment). For a specific tumor type, a decision will be made based on the calculated probability as given below:

1. Accrual to a tumor type (with minimum sample size requirement described above) will cease for futility if it is very unlikely (posterior probability <20%) that the response rate for the tumor type is “clinically meaningful” (\geq C2 threshold in [Table 10-1](#))
2. Otherwise, recruitment will continue until the next IA is performed or a maximum of 30 patients in that tumor type has been enrolled.

For the purpose of the IA, if a patient is still on study and the last available efficacy assessment is a PR/CR which is yet to be confirmed by a subsequent scan, then this patient will be considered as a responder.

The results at the final analysis within a tumor type will be regarded as positive if the posterior mean ORR is greater than the threshold for clinically relevant activity and the posterior probability of not being clinically meaningful is low (less than 10%).

Depending on enrollment, there may be multiple interim analyses.

Japanese safety run-in part

No formal interim analyses are planned. However, the dose-escalation design for safety run-in part foresees that decisions based on the current data are taken before the end of the planned safety run-in part. Details of this procedure and the process for communication with Investigators are provided in [Section 4.1.4](#).

10.8 Sample size calculation

Part 1:

The design of this part is adaptive in nature; hence, the final sample size is not fixed. A minimum of 10 evaluable patients and a maximum of 30 treated patients in each tumor type T1 through T13 will receive treatment. Thus, the total sample size across all tumor types will be between 130 and 310.

Patients will be continuously accrued, and, the accumulated data will be analyzed at interim as described in [Section 10.7](#). Based upon the results of any of these analyses, enrollment into one or more tumor types may be terminated.

The operating characteristics for this Bayesian Design are evaluated using simulation. Simulation-based probability estimates (relative frequencies) of futility at interim and positive results at final analysis for each tumor type in four scenarios (see [Table 14-12](#)) are provided in [Appendix 4](#). The number of simulations generated for each scenario is 1000. For additional details, please see [Appendix 4](#). Presented below is a summary of the operating characteristics based on eight tumor types included in the initial protocol design prior to interim analysis:

[Table 14-13](#) (Scenario 1) presents the operating characteristics of the design when the true underlying ORR of none the eight tumor types is clinically meaningful (in other words, null case for all tumor types). The false positive rate (for final analysis) for each of the tumor types are appropriately controlled, ranging between 2.6% and 6.8%. Similarly, the chances of stopping for futility at IA are high, ranging from 45.8% to 69.7%.

[Table 14-14](#) presents the operating characteristics for two scenarios (2a and 2b):

- Scenario 2a presents the operating characteristics when the true underlying ORR of all the eight tumor types is clinically meaningful (in other words, alternative case for all tumor types). The probability of positive conclusion (for final analysis) for each of the tumor types are appropriately high, ranging between 78.2% and 90.7%. Similarly, the chances of stopping for futility at IA are low, ranging between 3% and 11.9%.
- Scenario 2b, in contrast to Scenario 2a, presents the case where, out of all eight tumor types there is one single tumor type (T4-Bladder) which does not have clinically meaningful ORR while all other seven tumor types have clinically meaningful ORR. However, the model adapts appropriately and the false positive rate (1.1%) for T4 is

effectively controlled. For the rest seven tumor types which have clinically meaningful ORR (same as Scenario 2a), the probability of positive conclusion has slightly changed (vs Scenario 2a) but remained acceptably high (ranging between 79.6% and 88.7%).

Table 14-15 (Scenario 3) presents the operating characteristics when four tumor types have clinically meaningful ORR while the other four do not have clinically meaningful ORR. In this scenario as well, the false positive rates for the inactive tumor types are properly controlled (4.9% - 6.9%) while the probability of positive conclusion for the active tumor types are high (78.2% - 86.6%).

Similar operating characteristics are expected based on the thirteen tumor groups.

Part 2:

At least 20 patients will be enrolled in each of the dosing schedules. Table 10-3 shows the posterior mean and corresponding 90% credible interval for N = 20 (since it is planned to have approximately 20 patients in each schedule) for various observed ORR using a minimally informative unimodal beta prior distribution with parameters $a = 1/3$ and $b = 1$ (note: this assumes a priori response rate of 25%). This is same for all dosing schedules.

Table 10-3 Posterior summaries for given number of responses (ORR)

Observed ORR (N, %)	Posterior mean (90% credible interval)	Probability of no improvement [0% - 20%]	Probability of limited improvement [20% - 33%]	Probability of clinically meaningful improvement [33%-100%]
0 (0%)	0.016 (0.00,0.070)	0.999	0.001	0.000
3 (15%)	0.156 (0.051, 0.299)	0.744	0.228	0.028
4 (20%)	0.203 (0.081, 0.356)	0.534	0.385	0.080
5 (25%)	0.250 (0.115, 0.414)	0.316	0.498	0.185
10 (50%)	0.484 (0.311, 0.657)	0.002	0.070	0.928
15 (75%)	0.718 (0.548, 0.863)	0	0	1
20 (100%)	0.954 (0.866,0.997)	0	0	1

From Table 10-3, with a sample size of 20 patients, if the observed ORR is 25%, the probability of true ORR to be at least 33% is 18.5%. If the observed ORR is 50%, the probability of true ORR to be at least 33% is 92.8%. Also, with a sample size of 20, if the observed ORR is 15%, the probability of true ORR to be less than 20% is 74.4%.

Table 10-4 shows the posterior probability that ORR for schedule 1 (S1) is greater than ORR for schedule 2 (S2) for various observed ORR using a minimally informative unimodal beta prior distribution with parameters $a = 1/3$ and $b = 1$. Similar approach can be used to compare schedule 2 to schedule 3 and schedule 1 to schedule 3.

[figure not shown]

Table 10-4 Posterior probability that schedule 1 (S1) has higher ORR than schedule 2 (S2)

[figure not shown]
Observed ORR in S1 (N, %)	Observed ORR in S2 (N, %)	Posterior mean of the difference (90% credible intervals)	Probability that ORR in S1 is greater than ORR in S2 given data
3 (15%)	0 (0%)	0.141 (0.027, 0.287)	0.981
4 (20%)	3 (15%)	0.046 (-0.142, 0.236)	0.660
5 (25%)	4 (20%)	0.047 (-0.160, 0.254)	0.646
5 (25%)	5 (25%)	0.000 (-0.213, 0.212)	0.499
10 (50%)	5 (25%)	0.234 (-0.001, 0.459)	0.949
10 (50%)	8 (40%)	0.095 (-0.152, 0.336)	0.740
15 (75%)	10 (50%)	0.235 (-0.003, 0.463)	0.948
15 (75%)	12 (60%)	0.140 (-0.094, 0.371)	0.839
20 (100%)	15 (75%)	0.235 (0.071, 0.414)	0.990

From Table 10-4, with a sample size of 20 patients in each schedule, the posterior probability that ORR in S1 is greater than ORR in S2 is 50% if the difference between observed ORR in the two schedules is 0% respectively. However, if the difference between observed ORR in S1 and S2 is 5% respectively, the posterior probability that ORR in S1 is greater than ORR in S2 is approximately 65.0%. If the difference between observed ORR in S1 and S2 is 25% respectively, the posterior probability that ORR in S1 is greater than ORR in S2 is approximately 95.0%.

Table 10-5 Posterior probability that schedule 1 (S1) has higher ORR than both schedule 2 (S2) and schedule 3 (S3)

Observed ORR in S1 (N, %)	Observed ORR in S2 (N, %)	Observed ORR in S3 (N, %)	Probability that ORR in S1 is greater than ORR in S2 and S3 given data
3 (15%)	0 (0%)	0 (0%)	0.963
4 (20%)	3 (15%)	3 (15%)	0.509
5 (25%)	4 (20%)	3 (15%)	0.568
5 (25%)	5 (25%)	5 (25%)	0.335
10 (50%)	5 (25%)	5 (25%)	0.911
10 (50%)	8 (40%)	5 (25%)	0.719
15 (75%)	10 (50%)	10 (50%)	0.906
15 (75%)	12 (60%)	10 (50%)	0.814
20 (100%)	15 (75%)	12 (60%)	0.990

From Table 10-5, with a sample size of 20 patients in each schedule, the posterior probability that ORR in S1 is greater than ORR in both S2 and S3 is 33.5% if the difference between observed ORR in the three schedules is 0% respectively. However, if the observed ORR in S1, S2 and S3 are 10%, 8% and 5% respectively, the posterior probability that ORR in S1 is greater than ORR in both S2 and S3 is 71.9%.

Part 3:

If initiated, 20 patients will be enrolled in each of the one or two tumor groups (max two) selected based on emerging data from Part 1 and Part 2. For the one or two tumor groups selected in Part 3, appropriate intervals will be defined and specified before any reporting activity in the statistical analysis plan. Novartis may decide to not open Part 3 for enrollment based on emerging data from Part 1 and Part 2.

As of protocol amendment 6, 20-30 patients will enroll in TNBC tumor group using NIR178 continuous dosing schedule in combination with PDR001. A second tumor group may be considered for Part 3 after completion of Part 1, see [Section 4.1.3](#).

A sample size of 10 patients treated at 160 mg BID FCT NIR178 in combination with PDR001 in TNBC tumor group in Part 3 provides a high probability, 77%, of observing 0 or 1 adverse event when the true incidence rate is 9%. ([Table 10-6](#)).

[figure not shown]
Table 10-6 Probability of detecting adverse events with specified incidence rate based on N=10 patients

Number of adverse events	AE incidence rate			
	0.05	0.09	0.12	0.15
0 or 1	0.91	0.77	0.66	0.54
2 or 3	0.09	0.22	0.32	0.41
>3	0.00	0.01	0.02	0.05

Regarding the efficacy of part 3, [Table 10-7](#) shows the posterior mean and corresponding 95% credible interval for N=20 for various observed ORR rates using a minimally informative unimodal beta prior distribution with parameters a=0.176 and b=1 for TNBC patients (Note: this assumes a priori response rate of 15%). From [Table 10-7](#), with a sample size of 20 patients, if the observed ORR rate is 15%, the probability of true ORR rate for TNBC patients to be at least 13% is 54.8%

Table 10-7 Posterior mean and 95% credible intervals for given ORR rates

ORR (N, %)	Posterior mean (95% credible interval)	Probability of no improvement [0% - 5%]	Probability of limited improvement (5%-13%)	Probability of clinically meaningful improvement [13%-100%]
0(0%)	0.008 (0.00,0.066)	0.958	0.038	0.004
2 (10%)	0.103 (0.015, 0.259)	0.220	0.495	0.285
3 (15%)	0.150 (0.036, 0.326)	0.060	0.392	0.548
4 (20%)	0.197 (0.062, 0.386)	0.012	0.217	0.771
5 (25%)	0.244 (0.091, 0.443)	0.002	0.092	0.906
10 (50%)	0.481 (0.277, 0.688)	0.000	0.000	1.000

Japanese safety run-in part

The period for evaluating DLTs will be cycle 1 (i.e. the first 28 days of treatment with single agent NIR178 or in combination with PDR001). The safety run-in will evaluate three NIR178 dose levels sequentially. Each dose level may consist of 3 to 6 newly enrolled patients who have tumor histologies specified in [Section 5](#), and meet all other inclusion/exclusion criteria. The dose escalation is detailed in [Section 4.1.4](#).

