2.2 Rationale for the study design

This open label phase II study has three parts: Part 1: Multi-arm Bayesian adaptive signal finding design of NIR178 (dosed continuously) in combination with PDR001 in solid tumors and diffuse large B cell lymphoma (DLBCL); Part 2: Exploration of continuous and intermittent schedules of NIR178 in combination with PDR001 in patients with advanced NSCLC; Part 3: Further evaluation of efficacy of the best performing dosing schedule of NIR178 in combination with PDR001 in one or two tumor groups selected from Parts 1 and 2. The tumor group(s) selected for Part 3 will be based on emerging data from Part 1, Part 2 and latest scientific literature. Parts 1 and 2 will enroll in parallel. As of protocol amendment 6, enrollment in Part 2 has been completed, and the continuous dosing schedule of NIR178 has been selected as the preferred dose regimen as clinical efficacy results do not support the hypothesis that intermittent dosing improves NIR178 + PDR001 antitumor activity. Part 3 will be opened in parallel with Part 1, and will further assess TNBC patients with an IC score of 0 using NIR178 continuous dosing schedule in combination with PDR001. A second tumor group may be considered for Part 3 after completion of Part 1. Additionally, Part 3 will assess the safety and pharmacokinetics of a new FCT formulation of NIR178. The terms tumor types and groups are used interchangeably.

[figure not shown]
The purpose of Part 1 is to broadly evaluate the efficacy of NIR178 and PDR001 in 11 selected solid tumors and diffuse large B cell lymphoma (DLBCL) using a Bayesian adaptive signal finding design that utilizes predetermined futility/expansion thresholds to best identify tumor types that warrant further study with the combination. Tumor types were selected based on presence of features thought to be associated with adenosine mediated immunosuppression including, but not limited to, gene expression levels of CD73 and A2aR based on data from the Tumor Cell Genome Atlas (TCGA).

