4.1.1 Part 1: Bayesian adaptive signal finding in solid tumors and DLBCL

Part 1 of the study will enroll patients in the following tumor groups: renal cell carcinoma (RCC) (IO naive and IO pretreated), pancreatic cancer, urothelial cancer, squamous cell carcinoma of head and neck cancer (HNSCC) (IO naive and IO pretreated), diffuse large B-cell lymphoma (DLBCL), microsatellite stable colorectal cancer (MSS CRC) (RAS wildtype and RAS mutant), triple negative breast cancer (TNBC), cutaneous melanoma (BRAF V600E) and metastatic castration resistant prostate cancer (mCRPC). Each tumor type will initially enroll at least 10 patients (with minimum requirements described in [Section 4.2](#)). Depending on whether or not pre-specified criteria for futility are met, each tumor group may enroll up to a maximum of 30 patients with the exception of the MSS CRC RAS mutant and RAS wildtype groups, in which 20 additional patients will be enrolled per group. Therefore, this part will enroll a minimum of 130 patients and may enroll a maximum possible total of 310 patients.

Accrual to each tumor type in Part 1 will be based on futility analyses of observed ORR rates via interim analyses (for details of timing on interim analysis, see [Section 4.2](#)). These analyses will allow borrowing of information across tumor types with a hierarchical model (see [Section 10](#)). The hierarchical model allows dynamic borrowing of information between groups such that more borrowing occurs across the groups that have similar ORR and less borrowing between groups which differ. In this way, the model is a compromise between the two alternate extremes of either a completely pooled analysis or a separate analysis in each group.

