1.1 Study design

This is an open-label multi-part, phase II study evaluating the combination of NIR178 and PDR001 in patients with advanced solid tumors and diffuse large B cell lymphoma (DLBCL). Patients will receive combination treatment, NIR178 + fixed PDR001 400 mg Q4W, until disease progression (assessed by investigator as per iRECIST ([Appendix 3](#)) for solid tumors, [Cheson et al \(2014\)](#) for DLBCL or PCWG3 guidelines for mCRPC), unacceptable toxicity, start of a new anti-neoplastic therapy, or discontinuation at investigator's or patient's discretion, lost to follow-up, death or study termination by the sponsor. All patients who discontinue from study treatment due to disease progression must have their progression clearly documented. All disease assessments will be performed locally by the investigator. [REDACTED]

Note: For the rest of the document, PDR001 400 mg Q4W will be referred to as 'PDR001'; patients receiving single agent (SA) NIR178 as 'SA patients' and those receiving combination treatment as 'combination patients'.

[figure not shown]
This phase II study has 3 parts ([Figure 1-1](#)). Parts 1 and 2 will enroll patients in parallel, and consequent to results from the two parts, Part 3 will open in not more than two select study

indications once recommended dose and dosing schedule is determined. The study parts have the following objectives:

- **Part 1:** Multi-arm Bayesian adaptive signal finding design in groups of 13 treatment indications - 9 tumor types including DLBCL, with categories based on mutation status or prior IO treatment, and assigned continuous dosing of NIR178 (160 mg BID or following Protocol Amendment 5, 240 mg BID) in combination with PDR001.
Protocol Amendment 5 mandated administration of NIR178 240 mg BID + PDR001 in all newly enrolled patients having any of the Part 1 indications or 2 newly added indications, mCRPC and RCC IO-pretreated, leading to 13 groups (see Section 2.5.2).
- **Part 2:** Exploration of continuous and intermittent schedules of NIR178 160 mg BID in combination patients with advanced non-small cell lung cancer (NSCLC).
By the time Protocol Amendment 6 was formalized, this part was closed to enrollment and 'continuous' schedule was inferred as 'optimal'.
- **Part 3:** Further evaluation of 'optimal' NIR178 schedule (consequent to Part 2 results) in combination patients with selected Part 1 treatment indication.

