No formal interim analyses are planned. However, the dose-escalation design for safety run-in part foresees that decisions based on the current data are taken before the end of the planned safety run-in part. Details of this procedure and the process for communication with Investigators are provided in [Section 1.1.4](#).

3 Sample size calculation

3.1 Part 1

The design of this part is adaptive in nature; hence, the final sample size is not fixed. As of Protocol Amendment 6, a minimum of 10 and a maximum of 30 evaluable patients will have enrollment in 13 treatment indication groups (see [Section 2.5.2.1](#)). Thus, the total sample size across all treatment indications will be between 130 and 310.

Patients will be continuously accrued, and the accumulated data will be analyzed at interim as described in [Section 2.8](#). Based upon the results of any of these analyses, enrollment into one or more treatment indications may be terminated.

The operating characteristics for this Bayesian Design are evaluated using simulation. Simulation-based probability estimates (relative frequencies) of futility at interim and positive results at final analysis for each tumor type in four scenarios (see Protocol Table 14-12) are provided in Protocol Appendix 4. The number of simulations generated for each scenario is 1000. For additional details, please see Protocol Appendix 4. Presented below is a summary of the operating characteristics based on eight tumor types included in the initial protocol design prior to interim analysis:

Protocol Table 14-13 (Scenario 1) presents the operating characteristics of the design when the true underlying ORR of none of the eight tumor types is clinically meaningful (in other words, null case for all tumor types). The false positive rate (for final analysis) for each tumor type is appropriately controlled, ranging between 2.6% and 6.8%. Similarly, the chances of stopping for futility at IA are high, ranging from 45.8% to 69.7%.

Protocol Table 14-14 (Scenarios 2a and 2b):

- Scenario 2a presents the operating characteristics when the true underlying ORR of all the eight tumor types is clinically meaningful (in other words, alternative case for all tumor types). The probability of positive conclusion (at final analysis) for each tumor type is appropriately high, ranging between 78.2% and 90.7%. Similarly, the chances of stopping for futility at IA is low, ranging between 3% and 11.9%.

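### The stated Part 1 total of 130 to 310 does not follow from 10 to 30 patients in each of 13 groups: the minimum fits and the maximum does not

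*Protocol*

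**What the plan says.** Protocol 10.8 sets a minimum of 10 evaluable patients and "a maximum of 30 treated patients in each tumor type T1 through T13". It then draws the total: "Thus, the total sample size across all tumor types will be between 130 and 310". SAP 3.1 has the same structure, with "a minimum of 10 and a maximum of 30 evaluable patients will have enrollment in 13 treatment indication groups" followed by the same 130 to 310.

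Protocol 4.1.1 repeats the figures: "this part will enroll a minimum of 130 patients and may enroll a maximum possible total of 310 patients". It also qualifies the cap of 30, "with the exception of the MSS CRC RAS mutant and RAS wildtype groups, in which 20 additional patients will be enrolled per group". SAP 1.1.1 carries that exception too. Protocol 10.8 and SAP 3.1 do not mention it next to their totals.

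The counting unit is described in several ways. Protocol 10.4.2 and Table 10-1 list thirteen groups. Protocol 2.2 speaks of efficacy "in 11 selected solid tumors and diffuse large B cell lymphoma (DLBCL") and adds: "The terms tumor types and groups are used interchangeably". SAP 1.1 refers to "groups of 13 treatment indications - 9 tumor types including DLBCL".

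**The concern.** In Protocol 10.8 and SAP 3.1 the total is presented as a consequence of the sentence before it, so a reader will multiply it out. One end agrees and the other is 80 patients short. A planned sample size is a basic item that the study report will carry forward, and the same pair of numbers is printed in three places across two documents. As they stand, the text does not show which per-group rule produced the maximum, or how the colorectal exception and the 20 patients for T12 enter it.

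**Working it through.** **Inputs**
- 13 groups, T1 to T13 (Protocol 10.4.2, Table 10-1; SAP 2.5.2.1).
- 10 to 30 patients per group (Protocol 10.8; SAP 3.1).
- 20 additional patients in each of the two MSS CRC RAS groups, T9 and T10 (Protocol 4.1.1; SAP 1.1.1).
- 20 more RCC naive patients at 240 mg, T12, with no interim decision (Protocol Table 14-18, footnote).
- Nine tumor types when not split by mutation status, prior immunotherapy or dose (SAP 1.1).

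**Plan's own figure.** Minimum: 13 × 10 = 130, which reproduces. Maximum: 13 × 30 = 390, which does not reproduce 310 (390 − 310 = 80; 80/310 = 26%).

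**Alternative readings**

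| Reading | Minimum | Maximum |
|---|---|---|
| 13 groups at 10 to 30 | 130 | 390 |
| 11 non-CRC groups at 10 to 30, plus 2 × 20 CRC | 150 | 370 |
| 10 groups at 10 to 30, plus 3 × 20 (T9, T10, T12) | 160 | 360 |
| 12 groups listed in Protocol 4.1.1 at 10 to 30 | 120 | 360 |
| 10 non-CRC groups listed in 4.1.1, plus 2 × 20 CRC | 140 | 340 |
| 9 tumor types alone | 90 | 270 |
| 9 tumor types, plus 2 × 20 CRC | 130 | 310 |

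Only the last row matches both ends (9 × 10 + 40 = 130; 9 × 30 + 40 = 310).

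A count conditional on the data in Appendix 4 comes close at the top. Take T2, T4 and T5 at 14, 14 and 11, T6 at 30, and T9, T10 and T12 at 20 each. That sums to 129, and six remaining groups at 10 to 30 give 189 to 309. It misses the minimum and holds each CRC group at 20 in total, whereas Table 14-19 scenario 4 uses 27 and 28.

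**Protocol Table 14-19, 13-group final illustration.** Scenario 4, T1 to T13: 30 + 14 + 30 + 14 + 11 + 30 + 30 + 30 + 27 + 28 + 30 + 20 + 30 = 324, which is 14 above 310. Scenarios 1 to 3 total 243, 270 and 259.

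**Separate check of the Appendix 4 illustrations**
- Table 14-17, scenario 2: T7 and T8 both have 2/30 and the same prior, so they have the same posterior. P(ORR ≤ 10%) cannot be smaller than P(ORR ≤ 5%). Yet T7 (C1 = 10%) prints 0.1720 and T8 (C1 = 5%) prints 0.6188. Refitting the model by grid integration with the stated priors gives about 0.62 for T7 and 0.17 for T8, so the two C1 limits appear to have been exchanged.
- Table 14-19, scenario 4, T10: mean 0.2022 ≥ 0.13 and probability 0.0008 < 10%. Both success conditions of Protocol 10.4.2 are met, but the row reads Fail.
- Protocol 14.4.4 says that every not-clinically-meaningful probability in Table 14-17 scenario 2 exceeds 10%. T6, T9 and T10 print 0.0620, 0.0482 and 0.0350. They fail because their means (0.1088, 0.1149, 0.1246) are below 0.13.
- Six observed ORRs do not equal responders over patients. Table 14-10 scenario 2: T2, 0/9 shown as 16%. Table 14-18 scenario 2: T11, 1/10 as 8.3%. Scenario 3: T9, 3/14 as 0%; T10, 5/21 as 5.3%; T11, 2/10 as 16.7%. Scenario 4: T11, 2/10 as 16.7%. The correct values, in that order, are 0%, 10%, 21.4%, 23.8%, 20% and 20%.

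**The case against.** The strongest reply is that the total is informative only. No threshold, stopping rule or simulation uses 310, and SAP section 4 records that the study is closed out, so no enrollment turns on it. That stands, and it limits the weight of the point. It does not make the inference in Protocol 10.8 and SAP 3.1 correct.

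Several stronger readings are tempting, and the documents do not support them:
- *The true maximum is 390.* That follows only from the 10.8 rule taken without exceptions. Protocol 4.1.1 states an exception for CRC, and Table 14-18 gives T12 20 patients.
- *The sponsor counted nine tumor types.* This is an inference from a numerical match, and it needs the 40 CRC patients; nine types alone give 90 to 270.
- *CRC patients are double counted.* Protocol 14.4.4 records 17 MSS CRC patients before the RAS split, so 20 additional per RAS group can naturally mean on top of an earlier cohort.
- *The reader cannot tell whether the cap is per tumor type or per group.* Protocol 4.1.1, 4.2.1 and 10.8 and SAP 1.1.1 all state it per group. Nothing caps HNSCC or RCC at 30 overall.
- *The counts 9, 11 plus DLBCL, and 13 are rival sample-size rules.* They are largely nested: 11 solid groups plus DLBCL matches the 12 groups listed in Protocol 4.1.1, and the thirteenth comes from splitting RCC naive by dose. The terminology is loose, no more.

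On treated against evaluable, Protocol 10.4.3 and SAP 2.5.3 count patients who have discontinued treatment as evaluable at interim. The two caps would therefore nearly coincide with follow-up. The difference needs a clarifying statement and is not a material conflict.

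**Conclusion.** The maximum of 310 is wrong as a consequence of the rule printed beside it in Protocol 10.8 and SAP 3.1. The shortfall is 80 against the rule as printed, 60 if each RAS group is fixed at 20 (370), and 50 if T12 is also fixed at 20 (360). Under the last two readings the minimum would also change, to 150 or 160. Which range is right depends on a rule that the documents leave unsettled, so the supported conclusion is that rule and total must be reconciled.

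The 324 in Table 14-19 shows that the protocol's own illustration can exceed a total described as the maximum possible. It is one of four hypothetical scenarios, and the other three stay below 310.

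The Appendix 4 slips are real as printed. They sit in hypothetical illustrations and change no operative rule. A reader might take them as evidence against the decision rule or as support for the sample-size point; they are neither.

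**What to change.** Add a short table with the minimum and maximum for each of T1 to T13. It should settle three things: whether the 20 additional CRC patients per RAS group come on top of earlier CRC patients, the 20 for T12, and whether the cap counts treated or evaluable patients. Then restate the total in Protocol 4.1.1, Protocol 10.8 and SAP 3.1 as the sum of that table. Do not substitute 390 unless the 10.8 rule is confirmed to apply without exceptions.

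As separate minor corrections in Appendix 4:
- Recompute the Table 14-17 not-clinically-meaningful probabilities for T7 with C1 = 10% and for T8 with C1 = 5%.
- Change T10 in Table 14-19 scenario 4 to Success.
- Reword the 14.4.4 sentence on scenario 2 so that T6, T9 and T10 are said to fail on the posterior mean.
- Correct the six observed ORRs.

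The cost is text and table edits only, with no extra patients and no change to the decision rule.
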